#### 6.2.4. *Derived Data*

- Age (year), derived using first dose date as the reference start date and July 1st of birth year and truncated to a whole-year (integer) age. Patients whose derived age is less than 18 will have the required minimum age of 18 at informed consent; reporting for age, age groups, and lab ranges, however will be based on their derived age.
- Age group (<65, ≥65 years old)
- Age group (<65, ≥65 to <75, ≥75 to <85, ≥85 years old)
- Body Mass Index (BMI) (kg/m^2) = Weight (kg)/((Height (cm)/100))
- BMI category (<25 kg/m^2, ≥25 to <30 kg/m^2, ≥30 kg/m^2)
- The duration of AD from diagnosis (years) = [(Date of informed consent – Date of AD diagnosis )+1]/ 365.25.
  - If year of onset is missing, duration of AD will be set as missing. Otherwise, unknown month will be taken as January, and unknown day will be taken as 01. The duration of AD will be rounded to 1 decimal place.
- Duration of AD (years) category (0 to <2 years, 2 to < 5 years, 5 to <10 years, 10 to <20 years, ≥20 years)
- Diagnosis age (years), derived using diagnosis date as the reference start date and July 1 of birth year and truncated to a whole-integer age.
- Diagnosis age group (<18, ≥18 to <50, ≥50 years old)
- Change from baseline = postbaseline measurement at Visit x – baseline measurement.
  - If a baseline value is missing, it will not be imputed and the change from baseline will not be calculated.
- Percent change from baseline at Visit x:  
 ((Post-baseline measurement at Visit x - Baseline measurement)/Baseline measurement)\*100.
  - If a baseline value is missing, it will not be imputed and percent change from baseline will not be calculated.
- Weight (kg) = weight (lbs) \* 0.454.
- Weight category (<60 kg, ≥60 to <100 kg, ≥100 kg)
- Height (cm) = height (in) \* 2.54.
- Cyclosporine inadequate efficacy (yes, no)
  - Set **yes** if the reason for discontinuation is inadequate response.
- Cyclosporine intolerance (yes, no)
  - Set **yes** if the reasons for discontinuation are: intolerance to medication or contraindication (Physician indicated cyclosporine was used and a contraindication was noted).
- Cyclosporine contraindication [ineligible] (yes, no)

- Set to **yes** if cyclosporine never used because of a contraindication
- Cyclosporine inadvisable (yes, no)
  - Set to **yes** if the following reasons were selected for either not using the medication or discontinuing the medication:
    - Reason for not using medication: Physician decision, concern about side effects, unfavorable benefit risk, contraindication.
    - Reasons for discontinuation: inadequate response, intolerance to medication, or contraindication.
- TCNI inadequate efficacy (yes, no)
  - Set **yes** if the reason for discontinuation is inadequate response.
- TCNI intolerance (yes, no)
  - Set **yes** if the reasons for discontinuation are: intolerance to medication or contraindication (Physician indicated TCNI was used and a contraindication was noted).
- TCNI contraindication / [ineligible](yes, no)
  - Set to **yes** if TCNI never used because of a contraindication
- TCNI inadvisable (yes, no)
  - Set to **yes** if the following reasons were selected for either not using the medication or discontinuing the medication:
    - Reason for not using medication: Physician decision, concern about side effects, unfavorable benefit risk, contraindication.
    - Reasons for discontinuation: inadequate response, intolerance to medication, or contraindication.

### 6.3. Covariate Adjustment

The randomization to treatment groups at Week 0 (Visit 2) is stratified by disease severity (IGA) and geographic region as described in Section 5.1. Unless otherwise specified, the statistical analysis models will adjust for these stratification variables. The covariates used in the logistic model for categorical data will include the parameter value at baseline. The covariates used in the ANCOVA model for continuous data will include the parameter value at baseline. Inclusion of baseline in the model ensures treatment LSM are estimated at the same baseline value. When an MMRM analysis is performed, baseline value and baseline-by-visit interactions will be included as covariates.

### 6.4. Handling of Dropouts or Missing Data

Intercurrent events (ICH E9 R1) are events which occur after the treatment initiation and make it impossible to measure a variable or influence how it would be interpreted.

Depending on the estimand being addressed, different methods will be used to handle missing data as a result of intercurrent events. Intercurrent events can occur through the following:

- application of one of the censoring rules (including after permanent study drug discontinuation or after rescue therapy)
- discontinuation

- missing an intermediate visit prior to discontinuation or rescue
- lost to follow-up.

Non-censor intercurrent events are events that are not due to the application of any censoring rule, i.e., the last 3 items in the list above.

Note that as efficacy and health outcome data can accrue after a patient permanently discontinues study drug or begins rescue therapy, specific general censoring rules to the data will be applied to all efficacy and health outcome observations subsequent to these events depending on the estimand being addressed. These specific censoring rules are described below.

The *primary censoring rule* will censor efficacy and health outcome data after permanent study drug discontinuation or after rescue therapy. This censoring rule will be applied to all continuous and categorical efficacy and health outcome endpoints. This censoring rule is equivalent to using all the data up to rescue.

A *secondary censoring rule* will only censor efficacy and health outcome data after permanent study drug discontinuation. This sensitivity analysis will include all observed values up to study drug discontinuation. The secondary censoring rule will be applied to primary and key secondary efficacy and health outcome endpoints as sensitivity analyses.

Table JAIY.6.1 describes the planned imputation methods for efficacy and health outcome endpoints with associated censoring rules. Sections 6.4.1 through 6.4.5 summarize the methodology of each imputation rule.

**Table JAIY.6.1. Imputation Techniques for Various Variables**

Efficacy and Health Outcome Endpoints	Imputation Method
IGA(0,1), EASI75, 4-point Itch NRS improvement, EASI90, SCORAD75	NRI ab , pMI a , Tipping point a
EASI percent change, ADSS Item 2 change, Skin Pain NRS change	MMRM ab , mLOCF a , pMI a
All remaining categorical measures	NRI a
All remaining continuous efficacy and health outcome measures	MMRM a , mLOCF a

Abbreviations: ADSS = Atopic Dermatitis Sleep Scale; EASI = Eczema Area and Severity Index score; IGA = Investigator's Global Assessment for AD; mLOCF = modified last observation carried forward; MMRM = mixed model repeated measures; NRI = nonresponder imputation, NRS = Numeric Rating Scale; pMI = placebo multiple imputation; SCORAD = SCORing Atopic Dermatitis.

a Analyses utilizing the primary censoring rule.

b Analyses utilizing the secondary censoring rule.

### **6.4.1. Nonresponder Imputation**

A nonresponder imputation (NRI) method imputes missing values as non-responses and can be justified based on the composite strategy for handling intercurrent events (ICH E9 R1). This imputation procedure assumes the effects of treatments disappear after the occurrence of an intercurrent event defined by the associated censoring rule.

All categorical endpoints will utilize the NRI method after applying the primary censoring rule to patients who permanently discontinued study drug or were rescued (described in Section 6.4). Additionally, all primary and key secondary categorical endpoints will utilize NRI after applying the secondary censoring rule as sensitivity analyses. For analyses which utilize either of the censoring methods, randomized patients without at least 1 post-baseline observation will be defined as nonresponders for all visits.

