3.1. Background

Atopic dermatitis (AD), also known as atopic eczema, is a common, chronic, relapsing, highly symptomatic inflammatory skin disease (Bieber 2010). Patients with AD may present with skin lesions that can be acute with oozing, crusted, eroded vesicles or papules on erythematous plaques. Patients may also present with lesions that have a subacute appearance, with thick and excoriated plaques, or chronic appearance, with lichenified, slightly pigmented, excoriated plaques (Bieber 2010). Atopic dermatitis causes pruritus attacks throughout the day, which is the primary source of morbidity in this disorder (Simpson 2012). Pruritus often leads to an “itch–scratch” cycle, further compromising the epidermal barrier and resulting in dry skin, microbial colonization, and secondary infections (Krakowski et al. 2008); 36% of patients have reported that they often or always scratch until their skin bleeds (Langenbruch et al. 2014). Pruritus from AD can worsen during night time, resulting in sleep disturbances; approximately 27% of adult patients with AD experiencing sleep disturbance as a result of itching (Langenbruch et al. 2014). In adult patients with moderate to severe AD, sleep quality and latency were significantly associated with poor quality of life (QoL) (Yano et al. 2013).

In clinical practice, AD is classified as mild, moderate, or severe based on a variety of clinical features, including severity of skin lesions and pruritus, and extent of disease (body surface area [BSA] involved).

Until recently, there were no Food and Drug Administration (FDA)-approved systemic treatments for patients with moderate to severe AD, with the exception of systemic corticosteroids, and in the European Union, only cyclosporine had been approved for the treatment of patients with severe AD (Bieber and Straeter 2015). In 2017, Dupixent (dupilumab) injection, an IgG4 monoclonal antibody that inhibits interleukin (IL)-4 and IL-13, was approved by the FDA and the European Medicines Agency (EMA) for this patient population. A recently completed Phase 2 study (I4V-MC-JAHG [JAHG]) evaluated the safety and efficacy of baricitinib (a Janus kinase [JAK] inhibitor) in AD and results showed significant improvement in disease severity compared to placebo and no new safety concerns were identified (Guttman-Yassky et al. 2018).

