#### 4.2.2. Other Secondary Objectives

These are prespecified objectives that will not be adjusted for multiplicity.

Objectives	Endpoints
To test the hypothesis that baricitinib 2 mg QD + TCS or baricitinib 4 mg QD + TCS is superior to placebo + TCS in the treatment of patients with moderate to severe AD.	
 
• Proportion of patients achieving IGA of 0 or 1 with a <math>\geq 2</math>-point improvement at Week 4
 

To compare the efficacy of baricitinib 2 mg QD + TCS or baricitinib 4 mg QD + TCS to placebo + TCS in AD during the 16-week double-blind placebo-controlled period as measured by signs and symptoms of AD.	
 
• Proportion of patients achieving EASI50 at 16 weeks
 
• Proportion of patients achieving IGA of 0 at 16 weeks
 
• Mean change from baseline in SCORAD at 16 weeks
 
• Proportion of patients achieving SCORAD90 at 16 weeks
 
• Mean change from baseline in BSA affected at 16 weeks
 
• Proportion of patients developing skin infections requiring antibiotic treatment by Week 16
 
• Mean gram quantity of background TCS used over 16 weeks (tube weights)
 

To compare the efficacy of baricitinib 2 mg QD + TCS or baricitinib 4 mg QD + TCS to placebo + TCS in AD during the 16-week, double-blind, placebo-controlled treatment period as assessed by patient-reported outcome/QoL measures.	
 
• Percent change from baseline in Itch NRS at 2 days, 1 week, 4 weeks, and 16 weeks
 
• Mean change from baseline in Itch NRS at 2 days, 1 week, 4 weeks and 16 weeks
 
• Proportion of patients achieving a 4-point improvement from baseline in Skin Pain NRS at 16 weeks
 
• Mean change from baseline in the total score of the POEM at 16 weeks
 
• Mean change in the PGI-S-AD scores at 16 weeks
 
• Mean change from baseline in HADS at 16 weeks
 
• Mean change in the DLQI scores at 16 weeks
 
• Mean change in the WPAI scores at 16 weeks
 
• Mean change in the EQ-5D-5L scores at 16 weeks
 
• Mean number of days without use of background TCS over 16 weeks
 

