		pMI and Tipping Point	ITT	Bari 4 mg or Bari 2 mg vs PBO; Week 16	Sensitivity analysis
Body Surface Area (BSA) Affected by AD	
 
BSA score
 
Change from baseline in BSA score
 
	MMRM	ITT	Bari 4 mg or Bari 2 mg vs PBO; Week 16	Secondary analysis
		ANCOVA using mLOCF	ITT	Bari 4 mg or Bari 2 mg vs PBO; Week 16	Sensitivity analysis

Measure	Variable	Analysis Method (Section 6.2.3)	Population (Section 6.2.1)	Comparison/Time Point	Analysis Type
SCORing Atopic Dermatitis (SCORAD)	
 
• SCORAD score
 
• Change from baseline in SCORAD score
 
• Percent change from baseline in SCORAD score
 
	MMRM	ITT	Bari 4 mg or Bari 2 mg vs PBO; Week 16	Secondary analysis
		ANCOVA using mLOCF	ITT	Bari 4 mg or Bari 2 mg vs PBO; Week 16	Sensitivity analysis
	Proportion of patients achieving SCORAD75	Logistic regression using NRI	ITT	Bari 4 mg or Bari 2 mg vs PBO; Week 16	Key secondary analysis
			PPS	Bari 4 mg or Bari 2 mg vs PBO; Week 16	Sensitivity analysis
		Logistic regression using pMI	ITT	Bari 4 mg or Bari 2 mg vs PBO; Week 16	Sensitivity analysis
	Proportion of patients achieving SCORAD90	Logistic regression using NRI	ITT	Bari 4 mg or Bari 2 mg vs PBO; Week 16	Secondary analysis
		pMI and Tipping Point	ITT	Bari 4 mg or Bari 2 mg vs PBO; Week 16	Sensitivity analysis
Skin Infections	Proportion of patients developing skin infections requiring antibiotic treatment	Fisher's exact	ITT	Bari 4 mg or Bari 2 mg vs PBO; Week 16	Secondary analysis

Abbreviations: ANCOVA = analysis of covariance; Bari = baricitinib; ITT = intent-to-treat; mLOCF = modified last observation carried forward;

MMRM = mixed model repeated measures; NRI = nonresponder imputation; PBO = placebo; pMI=placebo multiple imputation; PPS = per protocol set.

Notes: (1) for all other post-baseline visits not mentioned in the table, but collected for the measures as specified in the protocol, the analyses will be made as exploratory analyses.

(2) All primary and key secondary analyses will be performed for Japan population. Other key secondary and exploratory analysis may be performed for Japan population.

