#### **6.15.5.6. Infections**

Infections will be defined using all the PTs from the Infections and Infestations SOC as defined in MedDRA. Serious infection will be defined as all the infections that meet the SAE criteria.

The number and percentage of patients with TEAEs of infections, serious infections, and infections resulting in permanent study drug discontinuation will be summarized by treatment group using MedDRA PTs. The proportion of patients developing skin infections requiring antibiotic treatment by Week 16 will also be summarized on the overview of infections table.

The number and percentage of patients with TEAEs of infections by maximum severity will be summarized by treatment group using MedDRA PTs.

Treatment-emergent infections will be reviewed in context of other clinical and laboratory parameters via a listing (details see Compound level safety standards).

The TEAE infections will be further analyzed in terms of potential opportunistic infection, herpes zoster and herpes simplex. Summary of HBV DNA monitoring results and association between infection and neutropenia/lymphopenia will also be provided in the context of infections.

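### The blanket censoring and nonresponder rules cover the antibiotic-treated skin-infection endpoint, which they do not fit, and leave undefined how censored patients are scored.

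*SAP*

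**What the plan says.** SAP 4.2.2 lists as an other secondary endpoint, not adjusted for multiplicity, "Proportion of patients developing skin infections requiring antibiotic treatment by Week 16". Four places in the SAP then bear on how it is analysed.

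- **Censoring.** Section 6.4 defines the primary censoring rule, which drops efficacy data after rescue or permanent drug discontinuation, and says: "This censoring rule will be applied to all continuous and categorical efficacy and health outcome endpoints".
- **Imputation.** Section 6.4.1 says "All categorical endpoints will utilize the NRI method after applying the primary censoring rule to patients who permanently discontinued study drug or were rescued". Table JAIY.6.1 assigns the same treatment to "All remaining categorical measures". Section 6.12.2 sends secondary analyses to that table for their imputation method.
- **The endpoint's own row.** Table JAIY.6.5 lists "Proportion of patients developing skin infections requiring antibiotic treatment" with Fisher's exact test, ITT, each dose against placebo, Week 16, secondary analysis. It names neither NRI nor a censoring rule. Table JAIY.6.4, which defines the efficacy outcomes, has no entry for it.
- **The safety section.** Section 6.15.5.6 adds: "The proportion of patients developing skin infections requiring antibiotic treatment by Week 16 will also be summarized on the overview of infections table". Section 6.15 includes data after rescue in safety analyses and uses the safety population.

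**The concern.** The rules in 6.4 and 6.4.1 are built for favourable responses. The protocol's examples of NRI (Section 10.3.1) are IGA 0/1 and the EASI 50/75/90 responses. For those, a patient who is rescued or stops drug is counted as not having succeeded, and the direction is clear. Skin infection is unfavourable and accumulates over time, and neither feature suits the rule.

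First, infections that can be observed would be dropped. Rescue opens after 2 weeks (SAP 6.10), so up to 14 of the 16 weeks can be censored in a rescued patient. Topically rescued patients continue study drug (Protocol 7.7.4). Patients who stop drug should stay in the study to Week 16 (Protocol 5.1.2). Adverse events and concomitant medication are scheduled at every treatment visit. The loss may also be informative, because Protocol 3.1 describes the itch-scratch cycle as "resulting in dry skin, microbial colonization, and secondary infections".

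Second, the SAP says that "A nonresponder imputation (NRI) method imputes missing values as non-responses". For an infection it does not say whether that means infected or not infected. The programmer would have to choose, both for censored patients and for randomised patients with no post-baseline observation, whom 6.4.1 makes nonresponders at all visits. What is at stake is the one designated ITT comparison of skin infections between arms.

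**Working it through.** **Plan figures.** The plan gives no infection, rescue or dropout rate and no power for this endpoint. Its only power figure (89%, 30% v 10% on IGA 0/1, 100 per arm, Fisher's exact, two-sided alpha 0.025) reproduces as 89.1% by exact enumeration, but it does not bear on this point.

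**Does the rule reach the endpoint?** The endpoint is binary, sits in the efficacy tables and is labelled a secondary analysis. Sections 6.4, 6.4.1 and 6.12.2 and Table JAIY.6.1 are worded without exception. The endpoint's row is silent on NRI, but silence in Table JAIY.6.5 is not an exemption elsewhere: its MMRM rows name no censoring rule either, yet 6.4.2 censors them. Where the SAP wants special handling it writes it out, as for background TCS in 6.11.1. The literal reading is therefore that the rules apply, with a row that appears to point the other way.

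**What the choice does.** All inputs below are assumptions. Let r be the proportion rescued or stopped. Infection risk is 5% in patients never rescued or stopped and 20% in those who are, in both arms. A share s of the latter infections falls after the event.

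- All infections counted: 0.05(1 - r) + 0.20r
- Censored, scored uninfected: 0.05(1 - r) + 0.20r(1 - s)
- Censored, every rescued or stopped patient scored infected: 0.05(1 - r) + r

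Central case: r = 0.20 placebo, 0.10 baricitinib; s = 0.5.

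| Scoring | Placebo | Baricitinib | Difference |
|---|---|---|---|
| All infections | 0.04 + 0.04 = 8.0% | 0.045 + 0.02 = 6.5% | -1.5 points |
| Scored uninfected | 0.04 + 0.02 = 6.0% | 0.045 + 0.01 = 5.5% | -0.5 points |
| Scored infected | 0.04 + 0.20 = 24.0% | 0.045 + 0.10 = 14.5% | -9.5 points |

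**Range.** With r (placebo/baricitinib) of 10%/5%, 20%/10%, 30%/10% and 40%/20%, and s from 25% to 75%, the difference runs from -0.75 to -3.0 points with all infections counted, from 0.0 to -2.0 scored uninfected, and from -4.75 to -19.0 scored infected. The zero is built in: at s = 75% the retained risk in rescued or stopped patients, 0.20 x 0.25 = 5%, equals that of everyone else.

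**Equal true risk.** Keep r at 20%/10% and s at 0.5, and set baricitinib's risk in patients never rescued or stopped to (0.08 - 0.02)/0.90 = 6.67%, so that both arms total 8.0%. Scored uninfected: 6.0% v 0.06 + 0.01 = 7.0%, a difference of +1.0. Scored infected: 24.0% v 0.06 + 0.10 = 16.0%, a difference of -8.0. The sign itself depends on the scoring.

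**The case against.** The best defence is that the specific row should govern. SAP 6.12 says Table JAIY.6.5 supplies method and imputation. The main-analysis rows for the other categorical efficacy outcomes all specify logistic regression with NRI, and this one does not. Fisher's exact is the SAP's test for adverse events (6.2.3), so the row looks like adverse-event handling. That is a fair reading, and it is why the defect includes a conflict within the SAP. It does not settle the matter, because four general statements say otherwise and the row claims no exception.

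A reader might infer three stronger things that the documents do not support.

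- That missing data are scored in the wrong direction. The direction is undefined; no text says that a rescued patient counts as infected or as uninfected.
- That infections in poorly controlled patients disappear. Only those after rescue or permanent discontinuation are lost, and rescue cannot begin in the first 2 weeks.
- That the objective goes unanswered. The infection overview reports the same proportion with post-rescue data. It is, however, in the safety population, its event window closes 30 days after last dose (SAP 6.15), and it is not the designated ITT analysis. Nothing says which figure answers the objective if the two differ.

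It also stands that no document states that rescue will differ by arm, and that the central gap of 1.5 points is about 1.5 patients at 100 per arm.

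**Conclusion.** The point holds as a misfit between a stated rule and one endpoint, compounded by a conflict with that endpoint's own row and a missing derivation. Read literally, the designated ITT analysis drops infections after rescue or permanent discontinuation and fills the gap with a value that has no defined meaning for an unfavourable event. The between-arm difference then rests partly on a scoring choice that the SAP does not make.

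The size is illustrative only: -1.5 points becomes -0.5 or -9.5 under the central assumptions. It depends on assumed infection and rescue rates, on rescue or stopping being more frequent on placebo, and on part of the infections falling after the event.

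The consequence is limited. This is an other secondary endpoint outside the multiplicity scheme, and no primary, key secondary or sample-size conclusion depends on it. It is still worth correcting before unblinding, because a choice made afterwards could be made knowing its effect.

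**What to change.** In SAP 6.4, Table JAIY.6.1 and Table JAIY.6.5, exempt this endpoint from the primary and secondary censoring rules and from NRI. The secondary rule should be named because 6.12.2 extends it to secondary endpoints as a supplemental estimand.

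Add a derivation row to Table JAIY.6.4 that counts every antibiotic-treated skin infection from first dose through Week 16, whether or not the patient was rescued or stopped drug. State how patients lost before Week 16 are handled and report the number with incomplete follow-up by arm. Use the same event definition in the infection overview table of 6.15.5.6, so that any remaining difference between the two tables comes from the analysis population alone. A version censored at rescue can be kept as supportive.

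The cost is SAP wording and one table program; the data are already collected. The downside is that infections after rescue therapy are attributed to the randomised arm, which the supportive version helps a reader judge.
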